2.5 Summary

In conclusion, ABT-888, combined with chemotherapy or radiation, has demonstrated anti-tumor activity in orthotopic xenograft models of pediatric GBM and has shown an acceptable toxicity profile in adult and pediatric phase I trials. Available data suggests that PARP is over-expressed in multiple malignancies, including pediatric high-grade gliomas, and therefore inhibition of this target may overcome chemotherapy and/or radiation resistance. Given the dismal prognosis for children with DIPG, it is appropriate to evaluate the combination of ABT-888 and radiation, followed by maintenance therapy with ABT-888 and TMZ, in this patient population.

3. PATIENT SELECTION

3.1 Eligibility Criteria

The eligibility criteria listed below are to be interpreted literally and cannot be waived. No exceptions will be given. All clinical and laboratory data required to determine eligibility of a patient enrolled on this trial must be available in the patient's medical or research record.

3.1.1 Age

Patients must be ≤ 21 years of age at registration

3.1.2 Tumor

Patients with newly diagnosed diffuse intrinsic pontine gliomas (DIPGs), defined as tumors with a pontine epicenter and diffuse intrinsic involvement of the pons, are eligible without histologic confirmation. Patients with brainstem tumors that do not meet these criteria or not considered to be typical intrinsic pontine gliomas will only be eligible if the tumors are biopsied and proven to be an anaplastic astrocytoma, glioblastoma multiforme, gliosarcoma, anaplastic mixed glioma or fibrillary astrocytoma.

Note: Patients with juvenile pilocytic astrocytoma, pilomyxoid astrocytoma, gangliogliomas, or other mixed gliomas without anaplasia are not eligible. Patients with disseminated disease are not eligible, and MRI of spine must be performed if disseminated disease is suspected by the treating physician

3.1.3 Neurological Status

Patients must be able to swallow oral medications to be eligible for study enrollment.

3.1.4 Performance Status

Karnofsky \geq 50% for patients >16 years of age or Lansky \geq 50 for patients \leq 16 years of age. Patients who are unable to walk because of paralysis, but who are up in a wheelchair, will be considered ambulatory for the purpose of assessing the performance score. See Appendix A.

3.1.5 Prior Therapy

Patients must have not received any prior therapy other than surgery and/or steroids.

3.1.6 Organ Function

Patients must have normal organ and marrow function documented within 14 days of registration and within 7 days of the start of treatment as defined below:

- $>1,000/mm^{3}$ Absolute neutrophil count _
- >100,000/ mm³ (unsupported) – Platelets
- Hemoglobin >10g/dl (unsupported
- Total bilirubin ≤ 1.5 times upper limit of normal (ULN) for age
- <5 x institutional upper limit of normal for age - ALT(SGPT)
- Albumin $\geq 2g/dl$
- Creatinine clearance or radioisotope GFR ≥ 70 mL/min/1.73 m² or Serum creatinine based on age/gender as follows:

	Table 8					
Serum Creatinine for age/gender						
Age	Maximu Creatinin	m Serum e (mg/dL)				
	Male	Female				
1 to $<$ 2 years	0.6	0.6				
2 to < 6 years	0.8	0.8				
6 to < 10 years	1	1				
10 to < 13 years	1.2	1.2				
13 to < 16 years	1.5	1.4				
\geq 16 years	1.7	1.4				
The threshold creatinine va	lues in this Table were	derived from the				
Schwartz formula for estim	ating GFR (Schwartz e	t al. J. Peds,				
106:522, 1985) utilizing child length and stature data published by the						
CDC.		-				

T 11 0

3.1.7 Pregnancy Status

Female patients of childbearing potential must not be pregnant or breast-feeding. Female patients of childbearing potential must have a negative serum or urine pregnancy test.

3.1.8 **Pregnancy Prevention**

Patients of childbearing or child fathering potential must be willing to use a medically acceptable form of birth control, which includes abstinence, while being treated on this study.

3.1.9 Informed Consent

Signed informed consent according to institutional guidelines must be obtained. Assent, when appropriate, will be obtained according to institutional guidelines.

3.2 Exclusion Criteria

3.2.1 Concurrent Illness

Patients with any clinically significant unrelated systemic illness (serious infections or significant cardiac, pulmonary, hepatic or other organ dysfunction), that would compromise the patient's ability to tolerate protocol therapy or would likely interfere with the study procedures or results.

3.2.2 Inability to Participate

Patients with inability to return for follow-up visits or obtain follow-up studies required to assess toxicity to therapy.

3.2.3 Seizures

Patients with active seizures or a history of seizure are not eligible for study entry, with the exception of patients with documented febrile seizure.

3.3 Inclusion of Women and Minorities

Both men and women of all races and ethnic groups are eligible for this trial.

3.4 Treatment at Primary Institution

All experimental protocol therapy should be dispensed and all imaging studies obtained at the primary institution. Laboratory studies, excluding pharmacokinetic and biologic assays, may be performed at a CLIA certified laboratory of the investigator's choice.

3.5 Criteria to Start Therapy

Protocol therapy must begin no later than 30 days after the date of radiographic diagnosis or surgery, whichever is the later date.

All clinical and laboratory studies/assessments required to determine eligibility (excluding diagnosis of the tumor) must be performed within 14 calendar days prior to registration unless otherwise indicated. Imaging evaluations necessary to establish eligibility for study entry must be done within two (2) weeks prior to registration.

Patients must begin therapy no later than 7 calendar days after study registration. If more than 7 calendar days elapse between the date eligibility studies outlined in section 10 were obtained and the start date of treatment, then the following studies must be repeated prior to treatment:

- CBC with differential
- Bilirubin
- ALT (SGPT)
- Serum creatinine

If any of these repeat laboratory studies are outside the parameters required for eligibility or the patient's clinical condition worsens so they no longer meet eligibility requirements (labs may

again be repeated within 48-72 hours), then the patient will not be eligible for protocol therapy.

4. REGISTRATION PROCEDURES

4.1 General Guidelines

4.1.1 Prior to Consent

Prior to consent the protocol's status should be verified via the PBTC Protocol Status web page, to ensure the study is open to accrual.

4.1.2 Informed Consent

Informed consent must be obtained prior to patient registration.

Furthermore, consent should be obtained prior to the initiation of any clinical procedures or assessments performed for the purpose of determining protocol eligibility, which would not otherwise be consistent with the institution's standards of clinical practice.

4.2 Patient Registration

Patients must be registered prior to any protocol treatment. Patient registration is only available to authorized personnel using the PBTC automated registration system. The registration procedures are available in the CRA manual, which is posted on the PBTC members' website. The PBTC Protocol Coordinator may also be contacted at [contact] for assistance in the registration process.

Reservations may also be made through the registration system providing time to assess the patient's eligibility. Reservations will be held for a maximum of 7 calendar days by which time the patient must have been registered on study. The patient's reservation should be canceled as soon as it is determined that the patient is not eligible or that the family/patient has decided not to consent to the trial.

5. TREATMENT PLAN

5.1 Agent Administration

Treatment will be administered on an outpatient basis. Reported adverse events and potential risks are described in section 7. Appropriate dose modifications are described in section 6. No investigational or commercial agents or therapies other than those described below may be administered with the intent to treat the patient's malignancy.

All patients will receive ABT-888 plus radiation followed by maintenance therapy with ABT-888 plus TMZ during the Phase I study. The Phase I portion of this trial is a dose finding phase for ABT-888 during the radiation phase of therapy. The Phase II portion of this trial is an efficacy study. Patients will be given a diary (located on the PBTC-033 Protocol webpage) to record the date and time the study drug was taken as well as any comments (e.g. side effects, vomiting, missed doses). If emesis occurs within 10 minutes of administration of ABT-888 or TMZ, the dose should be repeated. A missed dose will not be made up, but the missed dose and reason for missing the dose should be recorded in the diary. The completed Patient dairy will be reviewed weekly during radiation and at each clinic visit during maintenance.

5.1.1 ABT-888 plus Radiation (Phase I)

Patients will receive ABT-888 throughout radiation therapy as outlined in Table 9. Radiation therapy will be administered by 3D-conformal or IMRT to a dose of 54 Gy in 30 daily fractions, treating 5 days per week (typically M-F each week) as outlined in section 5.1.4. Irradiation will not be interrupted for ABT-888 related DLTs unless clinically indicated.

_	Table 9							
	Schema – Radiation Phase of Therapy							уy
	Week	1	2	3	4	5	6	Week 7-10
ľ	ABT-888, BID	Twie	ce dail	Rest/				
Ī	Radiation Therapy	Ľ	aily, l	M-F, f	for 6-7	week	S	Evaluation

ABT-888 will be given twice daily, **Monday through Friday** during radiation therapy (6-7 weeks total). The first dose of ABT-888 should begin on the first day of radiation therapy, except for those children who require sedation for irradiation (see below). **Dosing will be based on the BSA determined at the beginning of radiation therapy.** The morning dose of ABT-888 should ideally be given 60-120 minutes prior to daily radiation treatment. For patients who require sedation for radiation treatment and are not able to take the oral medication due to local requirements for NPO prior to sedation, ABT-888 may be given nightly, and the daytime dose given shortly after the child awakens from sedation guidelines permit, then the morning ABT-888 dose should be taken 60-120 minutes prior to radiation. Periodic adjustments in the timing of twice daily ABT-888 administration are allowed if needed to accommodate patient/family convenience provided that the daytime dose is given as close to 60-120 minutes prior to daily irradiation whenever possible and adherence to an every 12-hour dosing schedule is attempted whenever possible.

For patients taking the oral solution, the dose of ABT-888 should be rounded to the nearest 1 mg (e.g. 1.4mg to be rounded to 1.0 mg and 1.5mg to be rounded to 2mg). Specific instructions for handling ABT-888 are provided **Appendix** B. For patients unwilling to take the oral solution of ABT-888, dosing tables for patients with BSA $\geq 1.0 \text{ m}^2$ who choose to take only capsules is located in **Appendix** D. Patients are not allowed to take a combination of capsules and the oral solution of ABT-888.

All patients from the Phase I portion of the study, after completing radiation treatment and ABT-888, will continue with maintenance therapy starting week 11, as outlined in section 5.1.3.

5.1.1.1 Dose-finding Period for the Phase I study

The observation period for DLTs (Course 1) during Phase I of the study includes the entire duration of radiation therapy (approximately 6 to 7 weeks, allowing for delays in XRT for holidays, mask adjustments, etc.) and the rest period between the end of radiation therapy and the start of maintenance treatment on week 11. Dose limiting toxicities are defined in section 5.2. Guidelines for dose modifications (if required) are provided in section 6.1.

5.1.1.2 Dose Escalations during ABT-888 and Irradiation

Dose Level 1 of ABT-888 during radiation treatment will be approximately 80% of the adult dose of 100 mg bid, which has been well tolerated. It is also expected that the 150 mg bid dose level in adults will be declared tolerable shortly. Dose escalation/de-escalation will be done using a standard phase I, 3 + 3 design in increments of approximately 30% (see Table 10 below). If the adult dose of 150 mg bid with radiation has been declared tolerable by the time this trial begins patient accrual, and the starting dose level of 50 mg/m² bid is also tolerated in children, we propose to proceed from dose level 1 directly to dose level 3 (85 mg/m² bid, equivalent to the adult dose of 150 mg bid). If dose level 3 is not tolerated, then we will de-escalate to dose level 2. If dose level 3 is tolerated, we will study dose level 4 only if supported by adult clinical data and PBMC PARP inhibition data from our ongoing trial.*

Table 10 ABT-888 Dose Levels During Radiation, Phase I of the Study					
Dose Level ABT-888 dose (mg/m ² /dose BID), M-F					
0	35 mg/m ² /dose BID				
1 (starting dose level)	50 mg/m ² /dose BID				
2	65 mg/m ² /dose BID				
3	85 mg/m ² /dose BID				
4 (pending supporting data)*	110 mg/m ² /dose BID				

There will be no intra-patient dose escalation during the irradiation phase of the study (ABT-888 and radiation treatment). Phase I of the study will be completed when MTD/recommended phase II dose of ABT-888 that can be safely administered with radiation has been determined.

5.1.2 Drug Administration during Radiation - Phase II

The Phase II portion of the trial is to evaluate the efficacy of ABT-888 and radiation therapy (at the maximum tolerated or recommended ABT-888 dose level from the Phase I study), followed by maintenance therapy with 10 cycles of ABT-888 and temozolomide in patients with newly diagnosed DIPG. Follow instructions for administering ABT-888 during radiation for the Phase II portion of the study as previously outlined in section 5.1.1.

5.1.3 Drug Administration - Maintenance Therapy (Phase I and Phase II) Maintenance therapy of ABT-888 and TMZ will begin approximately at week 11 (3-4 weeks after the completion of irradiation and ABT-888) provided that the patient's bone marrow, renal, and hepatic organ functions continue to meet on study criteria. ABT-888 will be given twice daily, with the morning dose given 60-120 minutes prior to the daily dose of TMZ. ABT-888 and TMZ will be given on day 1-5, and each course of treatment will be a minimum of 28 days in length (Table 11).

Table 11						
Schema- Maintenance Phase of Therapy						
Each Course	May receive a maximum of 10 courses					
Day	1	2	3	4	5	6-28
ABT-888, BID	x,x	x,x	x,x	x,x	x,x	Rest/Evaluation
Temozolomide, once daily	Х	Х	Х	Х	Х	Rest/Evaluation

All patients (Phase I and Phase II), will start maintenance therapy on week 11 with 25 mg/m² bid

of ABT-888 and 135 mg/m²/day of TMZ (the starting dose for maintenance therapy, Table 12), for 5 days every 28 days, which represent the recommended phase II doses from PBTC-027. **Dosing of ABT-888 and TMZ will be based on the BSA determined prior to each course.** Since this dose determination was based on children with refractory brain tumors, many of whom were heavily pre-treated, it is possible that children with newly diagnosed DIPG, who are chemotherapy naïve at entry, will tolerate higher doses of ABT-888 and TMZ during maintenance.

5.1.3.1 Intra-patient Dose Escalation of TMZ during Maintenance

In an effort to maximize the TMZ dose (and potentially the efficacy of the combination treatment) that can be administered with ABT-888 for each patient, **intra-patient dose escalation of TMZ will be studied only for patients with minimal toxicities, considered at least possible related, in each course.** These patients' TMZ dose will be escalated (per Table 12) to 175 mg/m²/day (Dose Level 2), and subsequently to 200 mg/m²/day of TMZ (Dose Level 3) if the toxicities observed after 1 course of protocol therapy at each dose level meet the defined criteria. In patients who are not eligible to dose escalate after course 1 due to greater than minimal toxicities, there will be no further attempts to escalate the dose of temozolomide. Patients eligible to dose escalate after course 1 but are not dose escalated due to site related issues may start dose escalation in a subsequent course provided they meet all criteria for dose escalation.

Dose escalation of TMZ is not allowed if any of the following conditions exist:

Hematological Toxicity

- > Grade 1 thrombocytopenia
- > Grade 2 neutropenia

Non-hematologic Toxicity

- Any grade 4 non-hematologic toxicity
- Any grade 3 non-hematologic toxicity with the exception of:
 - \circ Grade 3 nausea and vomiting of < 5 days
 - Grade 3 elevation of transaminases that returns to levels meeting eligibility criteria within 7 days of study drug interruption and does not recur upon restarting drug.
 - Grade 3 fever or infection of fewer than 5 days in duration
 - o Grade 3 hypophosphatemia, hypokalemia, hypocalcemia or
 - o hypomagnesemia responsive to oral supplementation
- Any grade 2 non-hematologic toxicity that persists for > 7 days and is considered medically significant or sufficiently intolerable by patients that requires treatment interruption.

Intra Patiant Dasa Escalati	Intra-Patient Dose Escalation of TMZ during Maintenance Therapy (Days 1-5 per 28 day cycle)								
Dose Level									
0	20 mg/m ² BID	135 mg/m ² /day							
1 (Starting Dose)	25 mg/m ² BID	135 mg/m ² /day							
2	25 mg/m ² BID	$175 \text{ mg/m}^2/\text{day}$							
3	25 mg/m ² BID	$200 \text{ mg/m}^2/\text{day}$							

Table 12

A patient who experience any dose-modifying toxicity (defined in section 6.2) during intrapatient TMZ dose escalation will not be dose-escalated again, and he/she will receive the remaining maintenance therapy at the highest dose level on which no dose-modifying toxicity was observed in that patient (for example, a patient who experiences any dose-modifying toxicity on Dose Level 2 will complete the remainder of maintenance therapy on Dose Level 1). Intrapatient dose escalation to a given dose level will be halted based on similar rules employed in traditional 3+3 designs, i.e. if 2 out of first 2-6 patients 4 out of first 12 patients, etc. experience dose modifying toxicities.

Patient specific dose de-escalations will occur as needed when dose-modifying toxicities arise (section 6.2). Dose level 0, namely ABT-888 at 20 mg/m² bid and TMZ at 135 mg/m², is provided to allow for one dose de-escalation for patients experiencing dose-modifying toxicities at Dose Level 1. Any patient who experiences dose-modifying toxicities at dose level 0 will be taken off protocol therapy.

5.1.3.2 *Criteria for starting subsequent courses - Maintenance*

Patients will start each subsequent course of maintenance therapy with recovery of ANC $\geq 1,000/\mu l$ and Platelet count $\geq 100,000/\mu l$.

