3	85 mg/m ² /dose BID				
4 (pending supporting data)*	110 mg/m ² /dose BID				

Upon completing radiation treatment and ABT-888, all patients from Phase I of the study will continue with maintenance therapy starting week 11, as outlined below.

Schema- Maintenance Phase of Therapy								
Each Course May receive a maximum of 10 courses								
Day	1	2	3	4	5	6-28		
ABT-888, BID x,x x,x x,x x,x Rest/Evalua						Rest/Evaluation		
Temozolomide, once daily x x x x x Rest/Evaluation								

Phase II Study

Phase II of the study will begin when the MTD/recommended phase II dose of ABT-888 in combination with radiation therapy has been determined from the Phase I study. Maintenance therapy will consist of ABT-888 and TMZ beginning at week 11 (3-4 weeks after the completion of radiation and ABT-888). Starting doses of maintenance therapy will be 25 mg/m² bid of ABT-888 and 135 mg/m²/day of TMZ, for 5 days every 28 days, which are the recommended phase II doses from PBTC-027. Since this dose determination was based on children with refractory brain tumors, many of whom were heavily pre-treated, it is possible that children with newly diagnosed DIPG, who are chemotherapy naïve at entry, will tolerate higher doses of ABT-888 and TMZ during maintenance. In an effort to maximize the TMZ dose (and potentially the efficacy of the combination treatment) that can be administered with ABT-888 for each patient, intra-patient dose escalation of TMZ will be studied only for patients with minimal hematologic toxicities in each course, defined as \leq Grade 1 thrombocytopenia and \leq Grade 2 neutropenia, and minimal non-hematologic toxicities not meeting the definition of dosemodifying toxicities in section 5.1.3.1, after their first course of maintenance therapy at Dose Level 1. These patients' TMZ dose will be escalated for Course 2 to 175 mg/m²/day (Dose Level 2), and subsequently (Course 3) to 200 mg/m²/day of TMZ (Dose Level 3) if the toxicities observed after 1 course of protocol therapy at each dose level meet the above criteria.

Intra-Patient Dose Escalation during Maintenance Therapy (Days 1-5 per 28 day cycle)						
Dose Level	ABT-888	TMZ Dose				
0	$20 \text{ mg/m}^2 \text{ BID}$	135 mg/m ² /day				
1 (Starting Dose)	$25 \text{ mg/m}^2 \text{BID}$	135 mg/m²/day				
2	25 mg/m ² BID	175 mg/m²/day				
3	$25 \text{ mg/m}^2 \text{ BID}$	200 mg/m ² /day				

TABLE OF CONTENTS

SUMN	ARY OF CHANGES	I
PROT	OCOL ABSTRACT AND SCHEMA	6
1. C	DBJECTIVES	

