6.2.1 Non-Hematologic Toxicity

- Any grade 4 non-hematologic toxicity
- Any grade 3 non-hematologic toxicity with the exception of:
 - \circ Grade 3 nausea and vomiting of < 5 days
 - Grade 3 elevation of transaminases that returns to levels meeting eligibility criteria within 7 days of study drug interruption and does not recur upon restarting drug.
 - Grade 3 fever or infection of fewer than 5 days in duration
 - Grade 3 hypophosphatemia, hypokalemia, hypocalcemia or hypomagnesemia responsive to oral supplementation
- Any grade 2 non-hematologic toxicity that persists for > 7 days and is considered medically significant or sufficiently intolerable by patients that requires treatment interruption

For any of the above non-hematologic toxicities during maintenance therapy, ABT-888 and TMZ will be withheld until the toxicity resolves to meet on study parameters (section 3.1.6), and the patient will restart ABT-888 and TMZ at the next lower dose level (see **Table 12**). Protocol therapy will be discontinued if a non-hematologic dose modifying toxicity occurs at dose level 0.

- 6.2.2 Hematological Toxicity
 - \geq Grade 3 thrombocytopenia
 - Grade 4 neutropenia
 - A delay of > 14 days in starting subsequent cycles of maintenance due to ANC < 1,000/mm³ and/or platelet < 100,000/mm³ (for example, a patient never experienced grade 3 thrombocytopenia, but his/her platelet count lingered between 50,000 to 100,000/ mm³ beyond 42 days after the start of the previous course of maintenance therapy)

For the hematologic toxicities outlined above that occur during maintenance therapy, ABT-888 and TMZ will be withheld until criteria described below are met, and ABT-888 and TMZ will be restarted at the next lower dose level (see **Table 12**). Protocol therapy will be discontinued if a hematologic dose-modifying toxicity occurs at dose level 0.

- a. \geq Grade 3 thrombocytopenia: Platelet transfusion is permissible and strongly encouraged for patients with dose-limiting thrombocytopenia to minimize risk of intra-tumoral hemorrhage. ABT-888 and TMZ should not be restarted until platelet count has recovered to \geq 100,000/mm³ (transfusion independent).
- b. Patients with grade 4 neutropenia may receive filgrastim (G-CSF) support only for documented infection and/or sepsis. ABT-888 and TMZ should not be restarted until the

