25 mg/m² ABT-888 and 135 mg/m² of TMZ with a possibility to escalate to 175 mg/m² and to 200 mg/m² of TMZ, if no unacceptable toxicities occur following 1 course of treatment at each of these dose levels (**Table 12**). More specifically, intra-patient dose escalation will only be considered if a patient meets the escalation criterion following the first course of TMZ as part of maintenance therapy. Intra-patient dose escalation will be assessed only in patients who are eligible to escalate and escalation to a given dose will be halted based on similar rules employed in traditional 3+3 designs, i.e. if 2 out of first 2-6 patients, 4 out of first 12 patients, etc. experience dose modifying toxicities during their first course of therapy at a given dose level. . This stopping rule will be applied for patients enrolled during the Phase I and Phase II components of the study. Even though these stopping rules will only be enforced during the first course of treatment at a given dose level for TMZ, we will periodically monitor for the occurrence of dose modifying toxicities in later courses and may revise this approach in the event that excessive toxicities are observed.

13.2 Phase II Study Design/Endpoints:

The primary efficacy endpoint of this phase II trial is overall survival defined as the time from initiation of therapy to the date of death from any cause or to the date patient was known to be alive for surviving patients. Progression-free survival (PFS) is a secondary endpoint and is defined as the time from initiation of treatment to the earliest date of failure (disease progression, death from any cause, or second malignancy) for patients who fail and to the last assessment date for patients who have not failed. Patients who start other anti-cancer therapy prior to disease progression will be censored in the Kaplan-Meier estimate of PFS as of the date the alternative therapy began. Patients who have not failed (died) at the time of analyses will be censored at their last date of contact in the Kaplan-Meier estimate of the PFS (overall survival) distribution.

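### After maintenance course 1, a patient with prolonged low-grade thrombocytopenia can meet both the TMZ escalation criteria and the dose-reduction rule

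*Combined protocol and SAP*

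**What the plan says.** **Escalation.** Section 5.1.3.1 introduces its exclusions with "Dose escalation of TMZ is not allowed if any of the following conditions exist". The hematologic items are "> Grade 1 thrombocytopenia" and "> Grade 2 neutropenia"; a non-hematologic list follows. Delayed count recovery does not appear. The Phase II part of the Abstract and Schema says that "intra-patient dose escalation of TMZ will be studied only for patients with minimal hematologic toxicities in each course" and defines minimal by the same two grade limits, again without a delay item. Both places say the TMZ dose of a qualifying patient will go up to Dose Level 2. Section 13.1.3 fixes the timing: "intra-patient dose escalation will only be considered if a patient meets the escalation criterion following the first course of TMZ".

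**Reduction.** Section 6.2.2 has three hematologic dose-modifying toxicities: grade 3 or worse thrombocytopenia, grade 4 neutropenia, and a delay of more than 14 days in starting the next course because ANC is below 1,000/mm³ and/or platelets are below 100,000/mm³. Its example of the third is a patient who never reached grade 3 but whose "platelet count lingered between 50,000 to 100,000/ mm³ beyond 42 days after the start of the previous course of maintenance therapy". The consequence is a restart of both drugs one level lower.

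**Link between the two.** Later in 5.1.3.1, a patient with "any dose-modifying toxicity (defined in section 6.2) during intrapatient TMZ dose escalation will not be dose-escalated again". The same section says de-escalation follows section 6.2 toxicities, and that Dose Level 0 exists for patients who have such toxicities at Dose Level 1.

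**The concern.** The non-hematologic exclusions in 5.1.3.1 have the same content as the dose-modifying list in 6.2.1, so a non-hematologic dose-modifying toxicity always blocks escalation. The hematologic lists do not match in this way: the delay item in 6.2.2 has no counterpart in 5.1.3.1 or in the Schema. A patient whose only problem is slow platelet recovery at a low grade passes the escalation test and also triggers the reduction rule.

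Two things are at stake. One is the dosing instruction for a child with delayed marrow recovery. The other is the feasibility of intra-patient escalation, a primary objective in both phases (sections 1.1 and 1.2). Section 13.1.3 assesses it only in patients eligible to escalate, and for this patient the text does not settle eligibility.

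**Working it through.** There is no sample size or power figure to reproduce. The check is whether any set of counts satisfies both rules at once.

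**Inputs**
- Minimum course length: 28 days (section 5.1.3).
- Delay rule: more than 14 days, for platelets <100,000/mm³ and/or ANC <1,000/mm³ (section 6.2.2).
- Escalation limits: thrombocytopenia no worse than grade 1, neutropenia no worse than grade 2 (section 5.1.3.1 and Schema).
- Grading: CTCAE v4.0 (section 5.2), whose cut-offs the protocol does not print. Assumed here: platelet grade 1/2 boundary 75,000/mm³ (varied below) and neutrophil grade 2/3 boundary 1,000/mm³.

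**Step 1, timing.** 28 + 14 = day 42, which agrees with the example in 6.2.2.

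**Step 2, platelets.** Let P be the lowest platelet count of course 1, with platelets still below 100,000 past day 42, and let B be the grade 1/2 boundary. Escalation is permitted if P ≥ B. The delay rule applies because platelets are below 100,000. Both hold when B ≤ P < 100,000.

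| Assumed boundary B (/mm³) | Platelet range meeting both rules |
|---|---|
| 50,000 | 50,000 to <100,000 |
| 60,000 | 60,000 to <100,000 |
| 75,000 | 75,000 to <100,000 |
| 90,000 | 90,000 to <100,000 |
| 100,000 or higher | none |

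At B = 75,000, the part of the 6.2.2 example between 50,000 and 75,000 is already barred from escalation as worse than grade 1. Only the upper part is in conflict.

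**Step 3, neutrophils.** If the grade 2/3 boundary is 1,000, an ANC below 1,000 is already worse than grade 2 and blocks escalation. The ANC half of the delay rule then creates no overlap.

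**Step 4, cause.** Without the delay item, reduction needs grade 3 or worse platelets or grade 4 neutrophils. Both are outside the escalation limits, so no patient meets both rules. The unmatched delay item is the only source of the overlap.

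**Step 5, consequence.** From Dose Level 1, Table 12 gives:

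| | ABT-888 (mg/m² BID) | TMZ (mg/m²/day) |
|---|---|---|
| 5.1.3.1 escalation, Level 2 | 25 | 175 |
| 6.2.2 reduction, Level 0 | 20 | 135 |

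**Step 6, does another sentence resolve it?** The bar on escalating again covers a toxicity that arises during TMZ escalation, and its example is a patient at Level 2. Course 1 at Level 1 precedes any escalation. Section 5.1.3.1 also rules out later attempts for patients not eligible after course 1, but the trigger is more than minimal toxicity, which the Schema defines by grade for hematologic events. The patient in Step 2 does not trip it.

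**The case against.** The best answer is that the intended reading is not hard to see. Section 5.1.3.1 itself sends section 6.2 toxicities to de-escalation and provides Level 0 for Level 1 patients. Section 6.2 says de-escalation should occur if any listed toxicity is present. The Abstract says dose-modifying toxicities are monitored to guide escalation. Section 6 requires the study chair to be notified of any proposed dose modification, so a patient more than 14 days late should come to central attention. Most of this stands: the text leans toward reduction and there is a check. What remains is that no sentence says such a patient fails the escalation criterion, and no order of precedence is given.

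Two stronger readings are tempting. A reader might infer that sites would in practice move the same child in opposite directions. The documents do not show that, because 5.1.3.1 also carries the reduction instruction and the study chair is involved. A reader might also infer that one or two such patients could decide whether escalation is halted for the trial. Section 13.1.3 does not support this. Its halting rule counts dose-modifying toxicities in a patient's first course at the dose level reached by escalation, so the delay at Level 1 is not a halting event. Such a patient could add to the count only if escalated despite 6.2 and then affected by a new dose-modifying toxicity at the higher level. The documents give no frequency for either step.

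**Conclusion.** The inconsistency is in the current text, but it is narrow. It concerns Dose Level 1 patients after course 1 whose platelets never fall below the grade 1/2 boundary yet remain under 100,000/mm³ past day 42. The lower limit of that window rests on the assumed 75,000/mm³; the existence of an overlap does not, since it disappears only at a boundary of 100,000 or higher. The absence of an ANC overlap rests on the assumed grade 2/3 boundary of 1,000/mm³. The documents do not give the frequency; given how specific the pattern is, it is probably low.

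The effect is limited to inconsistent dosing instructions for these patients and an undefined eligible-to-escalate status in the feasibility assessment. Overall survival, the sample size of 60 and the power are unaffected. It still merits correction, because it concerns dosing in children and the denominator of a primary feasibility objective.

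**What to change.** Reconcile the Phase II text of the Abstract and Schema with sections 5.1.3.1, 6.2.2 and 13.1.3 so that no patient can satisfy both the escalation and the reduction rule. State explicitly whether the sentence in 5.1.3.1 barring further escalation covers a dose-modifying toxicity in course 1 at the starting level. In 13.1.3, say whether a patient with the delay described in 6.2.2 counts as eligible to escalate. Which dose consequence applies is for the sponsor to decide. The cost is protocol wording only, with no change to sample size or to the survival analysis.
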